## 8.2. Subject Confidentiality

ViiV and all investigators will ensure adherence to applicable data privacy protection regulation. The research team at RTI-HS and any approved vendors will have access to pseudonymized individual data. Sites will maintain a subject identification log with the names/initials/identifiers of participants who consented to participate in the study and study subject ID. Sites will assign subject ID at time of participant enrollment. Subject identification logs will be maintained at the sites and will never be shared with the research team at RTI-HS, third parties, or ViiV. Additionally, the collected data (eCRF and individual questionnaires) will not contain any participant -identifying information to further protect confidentiality (for instance, age or year of birth will be collected in lieu of a full birth date). To comply with applicable data protection regulations, European Union (EU) and UK personal data will be collected and stored in the EU or UK and only staff dedicated to this project and located in EU will have access to these. Pseudonymized data sets will be transferred to the US. Finally, only aggregated data in the form of analysis tables will be made available to ViiV. Thus, any reports generated will not contain any participant identifiers.

## 9. LEGAL BASIS FOR PROCESSING INDIVIDUAL HUMAN DATA

The authors confirm that study data is Individual Human Data not owned by ViiV, but that the proposed use of the Individual Human Data aligns with the ‘purpose of use’ outlined in the source contract and/or the terms and conditions of use of the data source and it will comply with any specified prohibitions of use.

## 10. MANAGEMENT AND REPORTING OF ADVERSE EVENTS/ADVERSE REACTIONS

This study has safety objectives. Safety collection and reporting will correspond to the following study types:

The participant surveys represent study type 1: Primary data collection studies with or without sites/investigators with safety objectives where there is consent and/or data collection direct from individuals. This part of the study is able to identify solicited events only.

### Collection of Adverse Events/Reactions (Solicited Events)

Solicited Events are defined as adverse events related to the GSK/ViiV product under evaluation and identified for collection in the study database as per study objectives. A Safety Management Plan (SMP) will be developed as per VQD-WI-053775: Non-Interventional Study Safety Management Planning. The SMP will include more detailed definitions of AE types as well as details of the causality assessment. Reporting timelines and safety contact details will also be provided in accompanying SMP.

Solicited events must be collected in the study database and reported to GSK for entry into the GSK Safety database. All AEs/SAEs, pregnancies and incidents, systematically collected in the Participant Surveys, which will be based on closed ended questions only, according to study objectives and considered causally related to the GSK/ViiV product being evaluated (ADRs) should be reported to the GSK Safety department (timing and contact information provided in the safety management plan). For primary data collection studies, where there is direct collection of data from individuals, these will be classified as solicited individual case safety reports (ICSRs). Valid ICSRs will be managed, classified, and submitted for onward reporting to regulators in line with the appropriate time frames as detailed in the Safety Management Plan. These will also be summarised in interim, if applicable, and final study reports.

 A closed ended question is where a respondent can only choose a pre-set response.

### **Reporting of Adverse Events/Reactions (Spontaneous Events)**

Adverse events related to CAB+RPV LA cannot be reported due to interview/survey structure based on closed ended questions only. Study staff will be trained on how to report suspected adverse reactions if a individual should report them outside of the conduct of the study.

The site completed e-CRF represent study type 5: Secondary data collection studies including unstructured data with human review with safety objectives. These studies can identify solicited events in aggregate at study end but cannot identify spontaneous events.

### **Collection of adverse events/reactions (Solicited Events)**

Solicited Events are defined as adverse events related to the GSK/ViiV product under evaluation and identified for collection as per study objectives.

The purpose of the study is to monitor exposure to CAB+RPV LA and to evaluate persistence, adherence, discontinuation and virologic effectiveness among PWH receiving CAB+RPV LA regimen. For CAB+RPV LA regimen, pre-defined safety events of interest persistence, adherence, discontinuation and virologic effectiveness, will be systematically recorded in aggregate. These will be summarised in final study reports. This study is based on secondary use of existing health data and as such Individual Case Safety Reporting (ICSRs) to regulatory agencies is not required.

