	Q2M 2 nd initiation injection	Q2M continuation injection																
On-time	23-37	53-67																
Late	38-67	68-127																
Delayed (Short delay)	38-67	68-97																

Endpoint	Definition		
	Long delay (requiring re-initiation)	NA	98-127
	Requiring re-initiation/ Discontinuation	>67	>127
CVF	Proportion of participants with: 
 
▪ 2 consecutive HIV RNA VL <math>\geq</math> 200 copies/mL prior to/by assessment timepoint
 
OR
 
▪ 1 HIV RNA VL level <math>\geq</math> 200 copies/mL prior to/by assessment timepoint followed by core agent/regimen discontinuation within 4 months of HIV RNA VL level <math>\geq</math> 200 copies/mL
 
		
Virologic suppression	
 
▪ Proportion of participants with VL measurement <math><</math> 50 copies/mL during follow-up
 
		
Non-response	
 
▪ Not achieving re-suppression after CVF, consisting of VL <math>\geq</math>50 copies/mL following CVF with no VL of <math><</math>50 copies/mL following CVF
 
		
Secondary			
Injection site reactions	
 
▪ Proportion of participants with documented diagnostic code/diagnosis of injection site reaction or nodules attributed to administration of CAB+RPV LA
 
▪ Proportion of participants with Division of AIDS grading 1-4 to classify severity
 
		
Hypersensitivity reactions	
 
▪ Proportion of participants with documented diagnosis of Hypersensitivity, anaphylactic reaction, allergic reaction or drug allergy to CAB+RPV LA
 
▪ 2 or more events are reported from 2 or more of the following groups of signs/symptoms:                             
 
○ Rash, fever, gastrointestinal symptoms (nausea, vomiting, diarrhea, abdominal pain), constitutional symptoms (lethargy, fatigue, malaise, myalgia, arthralgia, general ill feeling) respiratory symptoms (dyspnea, sore throat, cough, chest x-ray changes, predominantly infiltrates, which can be localized)
 
 
 
▪ Cases where there is a negative rechallenge with CAB+RPV LA
 
▪ Cases where symptoms resolved (or did not worsen/result in withdrawal from the study)
 
		

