### **7.8.1. Site Training**

Investigators and study coordinators will be trained via an initial web-based training session on the protocol, including adverse event (AE) reporting, study flow, EDC system, documentation, site responsibilities and expectations, and any applicable study processes. Any new information relevant to the performance of this study will be forwarded to the medical staff during the study.

No on-site monitoring visits will be performed for this study unless there is a specific need to meet with the site team. Remote data monitoring will be conducted during the life of the study to ensure linkage and integrity between the eCRFs and the participant surveys and to identify missing or unclear data in the eCRFs and issue queries.

RTI-HS will closely monitor the participant recruitment and data collection on a regular basis. Specifically, RTI-HS will provide oversight of activities, including screening participants, recruiting and obtaining consent from participants, and completion of electronic surveys and eCRFs. RTI-HS will maintain regular communication with all sites and will assess progress and site performance and address any issues as they arise.

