**Reporting of adverse events/reactions (Spontaneous Events)**

This study is based on data previously collected for other purposes e.g., routine healthcare encounters. As such, there is no requirement for the collection and reporting of Individual Case Safety Reports (ICSRs). Although the study is based on human review of unstructured data, the nature of the secondary data protocol driven data collection and analysis does not allow for reporting of serious and non-serious AEs, pregnancy exposures, or incidents related to any GSK/ViiV product during the conduct of this research. In addition, the minimum criteria of identifiable patient, reporter, exposure and event, needed to report individual case safety reports may not be present in the information reviewed within the context of the study. The data also may lack an identifiable patient and reporter and may be insufficient to establish attribution between a potential safety event and an individual patient using a GSK/ViiV product.

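### Section 10 exempts site-recorded reactions in prospective participants from individual reporting on a secondary-use rationale that does not fit them, and its safety-event list omits the reactions of secondary objective 2

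*Protocol*

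**What the plan says.** Section 10 states that the study has safety objectives and splits safety handling into two streams.

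**Participant surveys.** These are classed as primary data collection. The first Solicited Events subsection covers "All AEs/SAEs, pregnancies and incidents, systematically collected in the Participant Surveys". Those judged causally related go to the sponsor's safety department as individual case reports and from there to regulators. The Spontaneous Events subsection that follows says that product-related adverse events cannot be reported through closed questions. It adds that staff will be trained to report suspected reactions that a participant raises outside study conduct.

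**Site eCRF.** This is classed as study type 5, secondary data collection: "These studies can identify solicited events in aggregate at study end but cannot identify spontaneous events". The second Solicited Events subsection gives the reason for not requiring individual reports, "This study is based on secondary use of existing health data", and places the summary in the final study reports. The closing Spontaneous Events subsection adds: "The data also may lack an identifiable patient and reporter and may be insufficient to establish attribution".

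**Elsewhere.** Secondary objective 2 (Section 6.2) estimates how often injection site and hypersensitivity reactions are documented. Section 7.3.2 defines the hypersensitivity endpoint through a "documented diagnosis of Hypersensitivity, anaphylactic reaction, allergic reaction or drug allergy to CAB+RPV LA", and the injection site endpoint through a documented code or diagnosis attributed to the injections. Section 8.2 says: "Sites will maintain a subject identification log with the names/initials/identifiers of participants who consented to participate". Section 7.8.1 gives sites an "initial web-based training session on the protocol, including adverse event (AE) reporting".

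**The concern.** The stream with the individual reporting duty lists no reaction among its outcomes. The stream that supplies the reaction endpoints is excused from that duty. The excuse is that the data already exist and may not identify a patient, a reporter or a link to the drug. For participants who enroll before their first injection, other sections of the protocol say the opposite.

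At stake is whether a site that records, say, an anaphylactic reaction in a prospective participant can tell from the protocol what to do with it. The text trains sites in adverse event reporting and also tells them that the eCRF design does not permit reporting. It lists safety events of interest among which no reaction appears. This concerns the handling of safety information, not the precision of an estimate.

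**Working it through.** The check is mainly a comparison of sections.

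**1. Whom the rationale covers.** Section 7.5 plans 250 participants already on treatment and 1,750 new initiators: 250 + 1,750 = 2,000. The prospective share is 1,750 / 2,000 = 87.5%; the retrospective share is 250 / 2,000 = 12.5%. Sections 7.2 and 7.2.1 enroll prospective participants before the first injection, and Section 8.1 requires consent before data collection. No record of a reaction to a study-regimen injection can exist when they enroll. Section 10 does not separate the two groups within the eCRF stream.

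**2. What the surveys list.** Section 7.3.2 names eleven patient-reported outcomes:

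| Outcome | Items |
|---|---|
| Reasons for initiating | 2 |
| Baseline adherence | 7 |
| WHOQOL-HIV BREF | 31 |
| Treatment-related worries and stigma | 4 |
| Treatment-related benefits | 7 |
| HIVTSQs | 12 |
| HIVTSQc | 12 |
| Treatment preference | 3 |
| Reasons for missed injections | 4 |
| Reasons for discontinuation | 3 |
| Social determinants of health | 7 |

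Counting each instrument once: 2 + 7 + 31 + 4 + 7 + 12 + 12 + 3 + 4 + 3 + 7 = 92 items. None of the eleven is labelled as a reaction, adverse event or pregnancy outcome. After baseline the surveys run at month 12 and at discontinuation, for prospective participants only (Section 7.4).

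**3. Where the reactions are recorded.** Both reaction endpoints in Section 7.3.2 rest on documented codes or diagnoses. These reach the database through the eCRF, which the investigator or authorized staff complete at enrollment, at two or more yearly follow-ups and at study end (Section 7.4).

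**4. The stated reasons against the rest of the protocol, for prospective participants.** The closing subsection of Section 10 says that the elements needed for an individual report may be absent.

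| Element | Section 10 | Elsewhere |
|---|---|---|
| Patient | may not be identifiable | the site log links each consented participant to a study ID (8.2) |
| Reporter | may not be identifiable | investigator or authorized staff enter the data (7.4) |
| Exposure | may be missing | initiating the regimen is an inclusion criterion (7.2.1) |
| Link of event to drug | may not be possible to establish | injection site endpoint requires attribution; hypersensitivity diagnosis is one to the regimen (7.3.2) |

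One qualification: the line of the hypersensitivity definition built on groups of symptoms does not repeat the tie to the drug.

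**5. The event list.** The second Solicited Events subsection defines solicited events by the study objectives. It then names adherence, persistence, virologic effectiveness and discontinuation as the safety events of interest. The safety objective in Section 6.2 is secondary objective 2, and neither of its two reaction types is on the list.

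**6. The remaining route.** The training for reactions raised outside study conduct concerns what a participant reports. It does not clearly cover a reaction that the site finds in the chart and enters in the eCRF.

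**The case against.** The best defence is that the eCRF is abstracted from routine-care records for everyone, so a reaction in a prospective participant is already charted when the site enters it. On that view the label follows the origin of the data, not the date of enrollment. Whether abstraction after consent counts as primary or secondary collection depends on definitions the protocol does not give, so 87.5% does not by itself prove misclassification. This stands. What it does not rescue is the set of reasons Section 10 offers, which steps 1 and 4 show to be at odds with other sections.

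A second defence is that the ID log never leaves the site (Section 8.2). The central database may then indeed lack an identifiable patient, and the text says only that it may. That is fair for the contractor and the sponsor, but not for the site that makes the entry.

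A third is that the Safety Management Plan, not shown here, will settle details. Section 10 leaves to it the event definitions, causality assessment, timelines and contacts. The exemption itself is fixed in the protocol.

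Four stronger readings are tempting and are not supported:

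- *The surveys contain no reaction question.* Item wording and answer options are not shown. A reaction could be an answer offered for stopping or for a missed injection. Nor does the survey paragraph promise to ask about every event: it covers whatever is "systematically collected in the Participant Surveys, which will be based on closed ended questions" in line with the objectives.
- *A site would send nothing.* The protocol provides adverse event training and a route outside study conduct; what sites would do cannot be settled from this text.
- *A serious reaction would stay unseen for a stated number of years.* The enrollment period is not given, and Section 4 plans three sets of interim tables from which reactions are not excluded.
- *The reaction frequency is biased low.* Objective 2 counts documented reactions, so uncharted mild ones lie outside the endpoint by definition.

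**Conclusion.** The point holds as an internal inconsistency with a bearing on participant safety. Three parts of Section 10 need reconciling with Sections 6.2, 7.2, 7.3.2, 7.4 and 8.2: the stream to which individual reporting is attached, the rationale for exempting the eCRF, and the list of safety events. The first two concern chiefly the 1,750 prospective participants; the third is a plain error whatever the cohort.

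The conclusion assumes that the eCRF is the only source of the reaction endpoints, since the protocol names no other. It also assumes that the undisclosed survey items do not amount to a reaction outcome, since none is listed. It does not depend on how regulators would classify the eCRF, and it changes no sample size, precision or analysis figure.

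**What to change.** Amend Section 10 as follows.

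1. In the eCRF subsections, limit the secondary-use wording, and the reasoning about missing patient, reporter and attribution, to data that pre-date enrollment.
2. State which stream carries individual reporting of related hypersensitivity and serious injection site reactions that sites record in prospective participants, under the Safety Management Plan, and make the site training in Section 7.8.1 match.
3. Replace the list of safety events of interest with the injection site and hypersensitivity reactions of secondary objective 2.
4. Align the survey paragraph with the outcomes in Section 7.3.2, so that it claims no more than the surveys ask. Adding closed reaction items to the month 12 and discontinuation surveys is an option, not a requirement.

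The cost is wording in Section 10 and in the Safety Management Plan, and a modest number of individual reports to process from sites already due to be trained. Endpoints, study size and analyses stay as they are.

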**Reporting of adverse events/reactions (Spontaneous Events)**

This study is based on data previously collected for other purposes e.g., routine healthcare encounters. As such, there is no requirement for the collection and reporting of Individual Case Safety Reports (ICSRs). Although the study is based on human review of unstructured data, the nature of the secondary data protocol driven data collection and analysis does not allow for reporting of serious and non-serious AEs, pregnancy exposures, or incidents related to any GSK/ViiV product during the conduct of this research. In addition, the minimum criteria of identifiable patient, reporter, exposure and event, needed to report individual case safety reports may not be present in the information reviewed within the context of the study. The data also may lack an identifiable patient and reporter and may be insufficient to establish attribution between a potential safety event and an individual patient using a GSK/ViiV product.

**11. PLANS FOR DISSEMINATING AND COMMUNICATING STUDY RESULTS**

The target audience for these data includes healthcare providers, health plan population-based decision-makers, and regulatory and health authorities.

Abstracts will be prepared for both the interim and final analysis, with a manuscript developed from the final data set. All publications will comply with the *International Committee of Medical Journal Editors (ICMJE)* guidelines. A final full study report will be submitted to the Sponsor. Study results will be submitted to scientific conferences and for peer-reviewed journal publication.

